### 13.2 Sample Size/Accrual Rate

The planned sample size is a minimum of 4 and a maximum of 18. The estimated accrual is two patients per month.

### 13.3 Analysis of Secondary Endpoints

The secondary endpoints include pathologic CR at the time of surgical resection, pERK/total ERK in PBMC and tumor, plasma TGF $\alpha$  level, pharmacokinetics of AZD6244 alone compared to in combination with capecitabine, and presence of mutations in tumor biopsies. Analysis of secondary endpoints will focus on samples obtained at the MTD (12 patients) with the goal of describing potentially useful measures for future testing in Phase II trials of sufficient power. Changes in TGF $\alpha$  level from pre to post treatment will be related to the probability of pathologic CR using logistic regression. Presence of activating *BRAF* or *RAS* mutations or inactivating *PTEN* mutations in tumor biopsies pretreatment will be related to the probability of pathologic CR using logistic regression. We will evaluate if a reduction in pERK in PBMC (flow cytometry) correlates to a reduction in pERK in tumor (IHC grading) after AZD6244 treatment with a Spearman Rank Correlation.

The final PK analyses will be the responsibility of Clinical Pharmacology and DMPK, Alderley Park, AstraZeneca, UK. The AZD6244, N-desmethyl and AZD6244 amide concentration-time data, along with the derived PK parameters, will be listed and summarized appropriately. Where data allow, the following PK parameters will be

determined following administration of AZD6244 alone and following administration of AZD6244 alone and AZD6244 & capecitabine together. Additional parameters may be determined if deemed appropriate:

AZD6244:  $C_{max}$ ,  $t_{max}$ ,  $AUC_{(0-12)}$ ,  $AUC_{(0-24)}$ ,  $AUC_{(0-t)}$ ,  $C_{min}$ ,  $CL/F$

N-desmethyl AZD6244 and AZD6244 amide:  $C_{max}$ ,  $t_{max}$ ,  $AUC_{(0-12)}$ ,  $AUC_{(0-24)}$ ,  $AUC_{(0-t)}$ ,  $C_{min}$ ,  $CL/F$ , AUC metabolite:parent ratio,  $C_{max}$  metabolite:parent ratio

The PK parameters will be derived using non-compartmental analysis. The maximum plasma concentrations ( $C_{max}$ ) and the time to reach the maximum plasma concentrations ( $t_{max}$ ) will be determined by visual inspection of the plasma concentration-time profiles. The area under the plasma concentration-time curve from zero to 12 hours post dose  $AUC_{(0-12)}$  and zero to 24 hours post-dose  $AUC_{(0-24)}$  will be calculated by the linear trapezoidal rule. The total oral clearance from plasma ( $CL/F$ ) after an oral dose will be calculated from the dose divided by the AUC during the appropriate dosing interval.

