### 1.2. Secondary Objectives

- To determine if changes in phosphorylated ERK (pERK) in peripheral blood mononuclear cells correlates to changes in pERK in rectal tumors in the setting of treatment with AZD6244.
- To obtain exploratory information regarding the pathologic complete response rate (pCR) obtained after treatment with the MTD of AZD6244 Hyd-Sulfate in combination with Capecitabine and 50.4 Gy of radiation.
- To determine if a reduction in phosphorylated ERK (pERK) in peripheral blood mononuclear cells correlates to similar changes in ERK phosphorylation in rectal tumors in the setting of treatment with AZD6244.
- To perform an exploratory analysis to determine if the presence of activating mutations in *RAS* or *BRAF* in tumor or changes in plasma transforming growth factor- $\alpha$  (TGF $\alpha$ ) levels and tumor pERK/total ERK with AZD6244 treatment alone and after AZD6244 in combination with Capecitabine and radiation predicts for tumor/nodal down staging or pCR

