## 2.2 **Other Agent(s)**

Capecitabine and radiation are frequently combined for the treatment of gastrointestinal malignancies. Capecitabine is a fluoropyrimidine carbamate that is an orally administered prodrug of 5'-deoxy-5-fluorouridine (5'-DFUR) that is converted to 5-fluorouracil (5-FU). 5'-DFUR is hydrolyzed to the active drug 5-FU by thymidine phosphorylase which is present in many tissues in the body. Thymidine phosphorylase is expressed in higher concentrations in some human carcinomas compared to surrounding tissues.

In the setting of rectal cancer, there is a growing experience of Capecitabine and radiotherapy in the neoadjuvant setting.(18) The maximum tolerated dose of Capecitabine is 800-825 mg/m^2 twice daily combined with 50.4 Gy of radiation.(19-22) Downstaging occurs in approximately 50-85% of patients receiving the combination of Capecitabine and radiation in the neoadjuvant setting for locally advanced rectal cancer. Pathologic complete response rates of 8-16% have been described with the combination, similar to that observed with the combination of 5-FU and radiation in this setting.(23, 24) The most common Grade 3 or higher toxicity observed with Capecitabine in this setting is diarrhea which may be observed in as many as 20% of patients.

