### 2.5.1 Evaluation of mutations in *KRAS*, *BRAF*, and *PTEN* in tumor tissue.

Activating mutations in *KRAS* and *BRAF* are thought to predict for single agent efficacy with MEK inhibition(42) and may also be implicated in radiation response with AZD6244. This will be an exploratory endpoint for this study as the number of patients included are small and we estimate that only 40% of participants will have activating mutations. PTEN status may predict for resistance to MEK inhibition.(43) We hypothesize that the presence of activation mutations in *KRAS* or *BRAF* will be positively correlated with pathologic CR rate while loss of PTEN will be negatively correlated with pathologic CR. The presence of activating mutations will be evaluated via DNA purification, amplification via polymerase chain reaction, and sequencing. For *KRAS*, codons 12 and 13 will be amplified. For *BRAF*, exon 15 will be amplified. This analysis will be performed on pretreatment specimens only. These assays will be performed by the laboratory of pathology, NCI. If sufficient additional tissue or DNA remains, PTEN exon 1-9 amplification will be completed in the laboratory of [name] followed by sequencing. This will be completed for tumors in which PTEN expression is not detected by immunohistochemistry.

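### Section 13.3 leaves downstaging and tumor pERK out of the response analyses that objective 1.2 calls for, and its logistic regression on pCR will often give no finite estimate in 12 patients (minor, exploratory secondary analyses only)

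*Combined protocol and SAP*

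**What the plan says.** The last objective in section 1.2 covers mutations, plasma TGF-alpha and "tumor pERK/total ERK with AZD6244 treatment alone and after AZD6244 in combination with Capecitabine and radiation predicts for tumor/nodal down staging or pCR". The Précis has a similar objective. That makes three kinds of predictor and two outcomes.

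Section 13.3 sets the population: "Analysis of secondary endpoints will focus on samples obtained at the MTD (12 patients". It then specifies:

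- TGF-alpha change against pCR, by logistic regression.
- BRAF, RAS and PTEN mutations, whose presence "in tumor biopsies pretreatment will be related to the probability of pathologic CR using logistic regression".
- For tumor pERK, a Spearman correlation to see whether a "reduction in pERK in PBMC (flow cytometry) correlates to a reduction in pERK in tumor (IHC grading" scoring).

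Section 13.3 has no downstaging endpoint and no rule for few or no pCRs. Section 11.2 describes the assessment of pCR only, and no section defines downstaging.

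The background rates are in section 2.2: "Pathologic complete response rates of 8-16% have been described with the combination" and "Downstaging occurs in approximately 50-85% of patients receiving the combination of Capecitabine and radiation". For mutations, section 2.5.1 says "we estimate that only 40% of participants will have activating mutations". On total size, section 13.2 says "The planned sample size is a minimum of 4 and a maximum of 18".

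**The concern.** There are two separate problems.

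First, part of a stated objective has no analysis. Of the two outcomes named, only the rarer is modelled. Tumor pERK change, for which patients are asked to give optional biopsies on day 8 and day 15, is compared with blood pERK but never with response.

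Second, the named model may fail. Ordinary logistic regression has no finite odds ratio for a binary marker when any cell of the two-by-two table is empty. With one or two pCRs expected, an empty cell is the usual case. Without a rule in 13.3, the substitute method would be chosen after the data are seen, and these results are meant to suggest markers for Phase II.

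**Working it through.** **1. The plan's own figure.** Section 4.2 requires at least 6 patients at the recommended dose and section 13.1 adds 6, so 6 + 6 = 12, as 13.3 states. The maximum in 13.2 also fits: 6 + 6 + 6 = 18.

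**2. Objective against analysis.**

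| Predictor in 1.2 | Against pCR in 13.3 | Against downstaging in 13.3 |
|---|---|---|
| RAS/BRAF mutation | logistic regression | none |
| TGF-alpha change | logistic regression | none |
| Tumor pERK/total ERK change | none | none |

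This comparison needs no numerical assumption.

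**3. Expected pCRs.** 12 × 0.08 = 0.96 and 12 × 0.16 = 1.92.

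**4. Binary marker (RAS/BRAF).** Inputs: n = 12, 40% mutated (2.5.1), pCR rate p, no true association. With m mutated patients, the maximum-likelihood odds ratio is finite only if both groups contain at least one pCR and one non-pCR:

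P(finite) = Σ over m = 1 to 11 of Bin(m; 12, 0.4) × [1 − p^m − (1−p)^m] × [1 − p^(12−m) − (1−p)^(12−m)]

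The estimate is undefined if there are no pCRs, only pCRs, or only one mutation group. The other non-finite cases give zero or infinity.

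**5. Continuous marker (TGF-alpha change).** With k pCRs, the estimate is not finite if k is 0 or 12, or if all pCRs lie at one end of the ranking, which has probability 2/C(12,k):

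P(not finite) = P(k = 0 or 12) + Σ over k = 1 to 11 of P(k) × 2/C(12,k)

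| | pCR 8% | 12% | 16% | 25% (assumed) |
|---|---|---|---|---|
| RAS/BRAF: undefined | 36.9% | 21.7% | 12.5% | 3.4% |
| RAS/BRAF: zero or infinite | 49.5% | 53.2% | 50.6% | 37.1% |
| RAS/BRAF: total not finite | 86.5% | 74.9% | 63.1% | 40.5% |
| TGF-alpha: not finite | 43.8% | 28.4% | 18.1% | 6.3% |
| P(0 or 1 pCR) | 75.1% | 56.9% | 40.5% | 15.8% |

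Sensitivity of the RAS/BRAF total to n, at pCR 8/12/16%: 75/57/42% if all 18 patients were used; 90/81/71% if only 10 of the 12 have a resection (an assumption).

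**6. What exact methods can show.** 12 × 0.40 = 4.8, so take 5 mutated and 7 not. The smallest two-sided Fisher p is 5/12 = 0.42 with one pCR and C(5,2)/C(12,2) = 10/66 = 0.15 with two. For a continuous marker, the smallest two-sided exact rank-sum p is 2/12 = 0.17 with one pCR and 2/66 = 0.03 with two. So it cannot reach 0.05 with fewer than two pCRs, which is the case in 75/57/40% of trials. With 0 of 12, the exact 95% upper limit is 1 − 0.025^(1/12) = 0.26.

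**7. Downstaging.** At the historical 50-85%, 12 × 0.50 = 6.0 to 12 × 0.85 = 10.2 patients would be downstaged. The formula in step 4 then gives no finite mutation odds ratio in 16% of trials at 50% and 66% at 85%. Downstaging is therefore less sparse than pCR at the low end of the range, but not at the top.

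**8. A three-level ordered outcome (none / downstaged / pCR).** At an assumed odds ratio of 10, taking the historical rates as those of unmutated patients, the power of an exact rank-sum test against Fisher on pCR is:

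| Downstaging, pCR | Ordered | Fisher |
|---|---|---|
| 50%, 8% | 30.0% | 16.0% |
| 50%, 16% | 33.5% | 23.4% |
| 70%, 12% | 26.6% | 21.2% |
| 85%, 8% | 17.4% | 16.0% |
| 85%, 16% | 25.0% | 23.4% |

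**The case against.** The strongest reply is that the protocol already says what these analyses are. Section 2.5 calls the correlates exploratory and mainly descriptive, section 2.5.1 admits small numbers, and 13.3 aims to describe measures for later, adequately powered trials. No error rate or decision depends on the odds ratios. This stands against any complaint about low power, and it keeps the severity low. It does not supply an analysis for a named outcome or predictor, nor say what is reported when the named model cannot be fitted.

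A second reply is that 1.2 offers downstaging or pCR as alternatives, that 11.2 evaluates residual disease in rectum and nodes, and that 4.1.4 sends specimens to NIH pathology. So what downstaging lacks is a definition and a sentence, not data. That is fair, and it is why the fix is cheap. But reading the two outcomes as alternatives does not help tumor pERK, which has no response analysis at all.

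Third, the 8-16% comes from treatment without AZD6244. A higher rate would ease the problem, but at an assumed 25% the RAS/BRAF estimate is still not finite in 40% of trials.

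Fourth, the replacement methods are themselves weak. Steps 6 and 8 bear this out: they give a defined result, not stronger evidence.

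**Conclusion.** The concern holds as a minor one. Objective 1.2 is only partly analysed, which follows from the text alone. The regression planned for pCR would have no finite RAS/BRAF odds ratio in 86/75/63% of trials at pCR 8/12/16%, and no finite TGF-alpha estimate in 44/28/18%. These figures assume 12 evaluable patients, 40% mutated, no true association and pCR at the historical rate. Surgery is outside the protocol and biopsies are optional, so fewer than 12 may be evaluable.

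The documents do not support three stronger readings that a reader might infer:

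- That the trial's main conclusions are at risk. The MTD and DLT endpoints use none of these models.
- That the trial is too small for its correlates. It claims no power for them.
- That adding downstaging, or an ordered outcome, would make the evidence strong. At an assumed odds ratio of 10 the ordered outcome has about 17-34% power against 16-23% for Fisher on pCR, and at 85% downstaging the gain is only 1 to 2 points.

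A side note, not needed for this conclusion: 13.3 uses PTEN mutation as a predictor, while the hypothesis in 2.5.1 concerns loss of PTEN, and sequencing is planned only for tumors without expression on immunohistochemistry. How unsequenced tumors are coded should be stated.

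**What to change.** Amend 13.3 as follows.

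1. Add downstaging as an outcome beside pCR, defined as the change from baseline clinical T/N stage (section 3.3.2) to pathologic T/N stage, in patients who have both. Report how many lack either, and list recurrent tumors (section 3.1.2) separately.
2. Add change in tumor pERK/total ERK at day 8 and day 15 as a predictor of downstaging and of pCR, with the number of paired biopsies.
3. Replace ordinary logistic regression for pCR. For binary markers, use the Fisher exact test with an exact odds-ratio interval, one-sided when a cell is empty. For continuous markers, use a descriptive listing with an exact rank-sum test, noting that it cannot reach 0.05 with fewer than two pCRs. The same methods can serve for downstaging.
4. With no pCRs, report only the rate and its exact interval (0 of 12: 0-26%).
5. State that all these results are descriptive and carry no multiplicity-adjusted claim.

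The ordered outcome is optional.

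The cost is small: an agreed downstaging definition, SAP wording and minor programming. Baseline staging, biopsies and pathology review are already planned, so no patients or procedures are added. The downside is a few more exploratory comparisons, and evidence that stays weak.

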#### Secondary

- To evaluate the pharmacokinetics of AZD6244 delivered alone and in combination with Capecitabine 825 mg/m^2 PO BID.
- To obtain exploratory information regarding the pathologic response rate obtained after treatment with the MTD of AZD6244 Hyd-Sulfate in combination with Capecitabine and 50.4 Gy of RT.
- To determine if changes in phosphorylated ERK (pERK) in peripheral blood mononuclear cells correlates to changes in pERK in rectal tumors in the setting of treatment with AZD6244.
- To perform an exploratory analysis to determine if the presence of activating mutations in *RAS* or *BRAF* in tumor or changes in plasma transforming growth factor- $\alpha$  (TGF $\alpha$ ) levels and tumor pERK/total ERK with AZD6244 treatment alone and after AZD6244 in combination with Capecitabine and RT predicts for down staging or pathologic response.

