#### 2.1.2.1 Pharmacokinetics

N-desmethyl is the active metabolite of AZD6244, which is 3 to 5 times more potent to the parent compound. An amide metabolite can also be detected in human plasma but is 40 to 50 fold less active than AZD6244. Single dose pharmacokinetics of AZD6244 and N-desmethyl have been characterized following dosing of both the free base suspension (study ARRY-0401) for dose levels between 50 to 300 mg and the

Hyd-Sulfate preparation (D1532C00005) for dose levels between 25 to 100 mg. The parameters described below are those obtained with the Hyd-Sulfate preparation. AZD6244 was absorbed relatively quickly across dose levels, with a median  $t_{max}$  of 1.5 hours. Plasma N-desmethyl AZD6244 concentrations/exposure followed a similar pattern to AZD6244 over time, although  $C_{max}$  and AUC values were <15% of the parent within each patient. Following the peak, AZD6244 concentrations decreased multi-exponentially with a mean half-life ( $t_{1/2}$ ) of 5 to 7 hours. The  $t_{1/2}$  of the N-desmethyl metabolite was 9 to 13 hours. Limited data is available for AZD6244 amide. Concentrations of this metabolite were variable within subjects and between subjects. The time to maximum concentration was highly variable among patients.

Study D1532C00020 evaluated the pharmacokinetics of AZD6244 in patients under fasting conditions and after a high fat meal. Geometric mean  $C_{max}$  and AUC were reduced by approximately 60% and 20% under fed conditions compared to exposure following AZD6244 taken fasted. There was a trend toward a later  $t_{max}$  in the fed condition. Based on these findings it is recommended that AZD6244 should be taken on an empty stomach.

Plasma pharmacokinetic parameters were similar for single and a multiple dosing (day 8, 15, and 22), suggesting minimal accumulation over time with twice daily dosing, consistent with the terminal half-life observed. A similar pharmacokinetic profile was observed on day 8 compared to day 1 supporting that the steady state was achieved in this time. The exposure of AZD6244 N-desmethyl followed a similar pattern. Exposure on multiple dosing was comparable within patients. Comparison of data from 7 or 14 days BID dosing suggest steady state was achieved by day 7.

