### 2.5.5 Pharmacokinetic Measurements

Blood samples (2 ml) for the determination of plasma AZD6244, N-desmethyl AZD6244 and AZD6244 Amide determination will be collected from patients in a comprehensive PK sampling schedule. Blood will be immediately placed on ice and the specimen transported to the laboratory of [name] for processing and storage. Analysis of plasma samples for the determination of AZD6244, N-desmethyl AZD6244 and AZD6244 Amide concentrations will be the responsibility of the Clinical Pharmacology

& DMPK(Drug Metabolism and Pharmacokinetics) Department, Alderley Park, AstraZeneca, UK. Specimens will be shipped in batches from [name] laboratory to Astra Zeneca's contract laboratory for analysis.

For once daily dosing (dose level -1)

- Day 4 or 5 (AZD6244 alone): Pre-dose (within 10 minutes of dosing), 30 minutes, 1 hour, 1 hour 30 minutes, 2, 4, 8, 12 and 24 hours post-dose (24 hour sample is pre- the next day's dose).
- Day 11 or 12 (AZD6244 + capecitabine + radiotherapy): Pre-dose (within 10 minutes of dosing), 30 minutes, 1 hour, 1 hour 30 minutes, 2, 4, 8, 12 and 24 hours post-dose (24 hour sample is pre- the next day's dose).

For twice daily dosing (dose levels 1 and 2):

- Day 4 or 5 (AZD6244 alone): Pre-dose (within 10 minutes of dosing), 30 minutes, 1 hour, 1 hour 30 minutes, 2, 4, 8 and 12 hours post-dose (12 hour sample is pre- the next day's dose).
- Day 11 or 12 (AZD6244 + capecitabine + radiotherapy): Pre-dose (within 10 minutes of dosing), 30 minutes, 1 hour, 1 hour 30 minutes, 2, 4, 8 and 12 hours post-dose (12 hour sample is pre- the next day's dose).

The actual sample time and date of all PK samples will be recorded.

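### Section 13.3 lists a CL/F for two metabolites that are never dosed, and names no within-patient estimate for its alone-versus-combination PK endpoint

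*Combined protocol and SAP*

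**What the plan says.** **Endpoint.** The précis lists a secondary objective: "To evaluate the pharmacokinetics of AZD6244 delivered alone and in combination with Capecitabine". Section 13.3 words the endpoint as a comparison: "pharmacokinetics of AZD6244 alone compared to in combination with capecitabine". Section 2.5.5 schedules a full profile on day 4 or 5 (AZD6244 alone) and again on day 11 or 12 in the same patients. It labels the second profile as AZD6244 with capecitabine and radiotherapy.

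**Analysis.** Section 13.3 says that the concentrations, "along with the derived PK parameters, will be listed and summarized appropriately". It names logistic regression for TGFα and mutations and a Spearman correlation for pERK, but no estimate or interval for the PK comparison. The final PK analysis is assigned to the manufacturer's clinical pharmacology group.

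**Metabolites.** The parameter list headed "N-desmethyl AZD6244 and AZD6244 amide" includes CL/F as well as the metabolite:parent ratios for AUC and Cmax. The only formula for CL/F is that it "after an oral dose will be calculated from the dose divided by the AUC during the appropriate dosing interval".

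**Twice-daily sampling.** Section 2.5.5 sets the last sample at 12 hours after the dose, then adds that the "12 hour sample is pre- the next day's dose". Appendix E repeats this. The once-daily schedule uses the same remark for its 24-hour sample.

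**The concern.** Dose divided by AUC gives an apparent clearance only for the substance that was dosed. N-desmethyl AZD6244 is formed from AZD6244 (section 8.1.1), and section 2.1.2.1 describes the amide as a metabolite too. If the plan is followed, the report will carry a clearance column for two compounds whose clearance cannot be obtained from these data. For N-desmethyl the figure will be large and could be misread as fast elimination, although section 2.1.2.1 gives it a longer half-life (9 to 13 hours) than the parent (5 to 7 hours).

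The second matter is an omission. The endpoint is a comparison and the data will be paired, but the text does not say that the pairing will be used or that the change in exposure will be estimated with an interval. Another organisation does the final analysis, so the written specification is what it will work from.

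The third is a label that does not fit twice-daily dosing if the morning dose is profiled.

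**Working it through.** **1. Number of patients.** Section 13.3 states 12 patients at the MTD. Section 4.2 requires at least 6 at the recommended dose and section 13.1 adds 6 more: 6 + 6 = 12, which reproduces the figure. The documents give no precision, power or variance for PK, so there is no other planned figure to reproduce.

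**2. What the metabolite figure measures.** Let D be the parent dose, AUCp the parent AUC and AUCm the metabolite AUC over the dosing interval.

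- Formula as written, for the parent: D/AUCp. For a metabolite: D/AUCm.
- Their ratio: (D/AUCm) ÷ (D/AUCp) = AUCp/AUCm, which is 1 ÷ (metabolite:parent AUC ratio).
- In terms of true metabolite clearance CLm, D/AUCm = CLm/(F × fm), where fm is the fraction of absorbed parent converted to that metabolite. Since fm is not known, CLm cannot be recovered.

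Section 2.1.2.1 reports that N-desmethyl "AUC values were <15% of the parent within each patient". So the ratio exceeds 1/0.15 = 6.67. For illustration, AUC ratios of 0.10 and 0.05 would give 10 and 20. For the amide, section 2.1.2.1 says only that data are limited and variable, so no multiple can be given.

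**3. Precision of the comparison, n = 12.** Let sw and sb be the within- and between-patient SDs of log AUC. Both are assumptions, because the documents give neither. The 90% interval is the estimated ratio divided and multiplied by a factor:

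- Paired: exp(1.796 × √2 × sw/√12), with t on 11 degrees of freedom.
- Treating the two days as separate groups: exp(1.717 × √(2/12) × √(sw² + sb²)), with t on 22 degrees of freedom.

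| Assumed sw / sb | Paired | Pairing ignored |
|---|---|---|
| 0.2 / 0.5 | exp(0.147) = 1.16 | exp(0.377) = 1.46 |
| 0.3 / 0.3 | exp(0.220) = 1.25 | exp(0.297) = 1.35 |
| 0.4 / 0.2 | exp(0.293) = 1.34 | exp(0.313) = 1.37 |

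Expressed by an assumed within-patient CV, with sw² = ln(1 + CV²), the paired interval is the estimate times 0.90 to 1.12 at 15%, and times 0.75 to 1.33 at 40%. A paired estimate is therefore workable at this size.

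**4. The 12-hour label.** I assumed a one-compartment oral model at twice-daily steady state, with half-life 5 to 7 hours and a peak at 1.5 hours, and applied the protocol's sampling times and the linear trapezoidal rule. A sample taken at 12 hours gives AUC(0-12) within 1% of the true value. If the last sample were instead drawn before the next morning's dose, and the curve interpolated from 8 to 24 hours, AUC(0-12) would be about 4 to 5% too high.

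**The case against.** The secondary analyses are explicitly descriptive, meant to find measures for later trials with adequate power. The design is already paired, individual values will be listed, and "will be listed and summarized appropriately" does not rule out within-patient ratios. This stands. A reader might infer that the plan intends an unpaired analysis and will lose the precision in the first row of the table. No section proposes that, and the contrast nearly vanishes in the third row. What remains is that an endpoint worded as a comparison has no named estimate.

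On metabolite CL/F, the formula does not name the compound dosed, the correct metabolite:parent ratios sit in the same list, and no dose decision uses the figure. These points limit the harm but do not make the parameter valid. The provision that parameters are derived where data allow does not screen it out, because the division can always be done. A reader might apply the 6.7-fold figure to both metabolites; the documents support it only for N-desmethyl.

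On the 12-hour sample, the nominal time is explicit and actual times are recorded. A morning dose is specified only for the once-daily level (section 4.1.1), and the label would be literally right for an evening profile. A reader might infer that AUC(0-12) and Cmin would be ruined. The working does not bear this out for AUC(0-12). At steady state a next-morning pre-dose sample is again a trough, so Cmin would hardly change.

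**Conclusion.** The concern holds, as a low-severity point with three parts of unequal weight.

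- **Metabolite CL/F is wrong as written.** It is not a clearance and adds nothing to the AUC ratio already listed. For N-desmethyl it exceeds 6.7 times parent CL/F. This rests on the inference that the dose means the AZD6244 dose, for which the documents offer no alternative.
- **The comparison is under-specified.** A named paired estimate is a clear improvement, but its size cannot be fixed: at n = 12 it ranges from 1.16 against 1.46 to 1.34 against 1.37, under assumed SDs. A reader might also take the ratio as the effect of capecitabine by itself. The documents do not support that, because radiotherapy has also begun by day 11 or 12.
- **The twice-daily label is a wording slip**, probably carried over from the once-daily schedule, with a small likely effect.

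**What to change.** 1. **Section 13.3, metabolite list:** delete CL/F for N-desmethyl AZD6244 and the amide. Keep the metabolite:parent AUC and Cmax ratios.
2. **Section 13.3, comparison:** state that for each patient with both profiles the log ratio (day 11 or 12 over day 4 or 5) of Cmax and AUC(0-12) will be calculated, and reported as a geometric mean ratio with a 90% confidence interval. Describe the contrast as AZD6244 with capecitabine and radiotherapy versus AZD6244 alone. No powered test is needed.
3. **Section 2.5.5 and Appendix E:** reconcile the twice-daily label with the nominal time by stating that the 12-hour sample is drawn before the next scheduled dose.

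The cost is a wording change and a short addition to the analysis. No further samples, visits or patients are needed.
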